Participants in the varenicline arm will receive a digital recommendation and support to use varenicline during their quit attempt, along with information on varenicline's benefits and potential side-effects, instructions for proper use, and guidance on how to obtain the medication either free of charge or with the standard NHS prescription charge. They will also be advised to access the Smoke Free app using a unique link provided to participants in the varenicline arm, where they will receive smoking cessation behavioural support and advice on the benefits of using varenicline during their quit attempt. One day after randomisation, they will receive an email with similar information on varenicline's benefits and potential side-effects, instructions for proper use and guidance for obtaining the medication and a reminder to use the Smoke Free app for smoking cessation behavioural support.

Cytisine arm

Participants in the cytisine arm will receive a similar digital recommendation to use cytisine during their quit attempt, along with information on its benefits and potential side-effects, instructions for proper use and guidance on obtaining the medication either free of charge or with the standard NHS prescription charge. They will also be advised to access the Smoke Free app using a unique link provided to participants in the cytisine arm, where they will receive smoking cessation behavioural support and advice on the benefits of using cytisine during their quit attempt. One day after randomisation, they will receive an email with similar information on cytisine's benefits and potential side-effects, instructions for proper use and guidance for obtaining the medication and a reminder to use the Smoke Free app for smoking cessation behavioural support.

The Smoke Free app will be restricted for participants who enrol in the study, and they will only be able to access it through the unique link based on their group allocation. If participants opt out of the study, they will regain normal access to the Smoke Free app.

Measures

Outcomes

The primary outcome will be percentage of participants reporting medication use (varenicline or cytisine use) at the 2-month follow-up. We will also report percentage of participants reporting varenicline or cytisine use among those recommended one of them at the 2-month follow-up.

Secondary outcomes will be percentage of participants reporting:
(i) continuous abstinence for one month assessed at 2-month follow-up.

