(ii) biochemically-verified continuous smoking abstinence for six months assessed at the 7-month follow-up by a) group allocation (cytisine vs varenicline vs control) and b) by use of recommended medication among those in the intervention arms. Following the Russell Standard, self-reported abstinence will be measured as not having smoked more than five cigarettes for the entire 6-month period preceding the 7-month follow-up (20). Analyses will follow the intention-to-treat principle. This means that all

participants will be analysed in the groups to which they were originally assigned, regardless of whether they completed the study or adhered to the intervention. Multiple imputation will be used to account for missing outcome data (i.e., participants who will be lost to follow-up or did not provide outcome data). As a sensitivity analysis, missing data will be treated as no medication users (for medication use outcomes) and smokers (for smoking cessation outcomes) in the analysis. Self-reported abstinence will be biochemically verified by measuring participants' CO levels via a video call with a researcher. A CO monitor will be sent to participants who self-report abstinence at 7-month follow-up and those with a CO reading of less than 8 parts per million will be classified as abstinent (21, 22).

The baseline questionnaire will assess the following:

Participants' contact details: e-mail address, mobile phone number.

Baseline

Sociodemographic characteristics:

age,

sex (male, female, other),

education (any versus no post-16 qualifications),

financial status (live comfortably, meet needs with little left, just meet basic expenses, do not meet basic expenses (23)),

country of residence (England, Scotland, Wales, Northern Ireland), ethnicity (Asian or Asian British background, Black, Black British, Caribbean or African background, White background, mixed or multiple ethnic groups (e.g., White and Black African or White and Asian), other ethnic group).

Smoking related characteristics:

number of cigarettes smoked per day,

cigarette addiction (first cigarette within 5, 6-30, 31-60 or >60 minutes of waking),

urges to smoke (How much of the time have you felt the urge to smoke a cigarette in the past 24 hours? (not at all, a little of the time, some of the time, a lot of the time, almost all the time, all the time); How strong have the urges been? (no urges, slight, moderate, strong, very strong, extremely strong)(24, 25),

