history of serious quit attempts (never, yes-not in the past year, yes-in the past year),

past and current use of support for smoking cessation (prescription nicotine replacement therapy (NRT), NRT bought over the counter, varenicline, bupropion, cytisine, e-cigarettes, face-to-face behavioural support, telephone support, written self-help materials, website, apps, none, other).

Procedure

Participants will be assessed at enrolment (baseline), two months and seven months after enrolment. Table 1 summarises the schedule of enrolment and follow-up assessments for trial participants.

Potential participants will have downloaded the Smoke Free app within the past week during the recruitment period and only those residing in the UK will see an on-screen message with information about the study and a link to access the baseline questionnaire via a weblink. Those who meet the

eligibility criteria, assessed via the questionnaire and complete the baseline survey, will be automatically randomised to the intervention or control arms.

All questionnaires will be conducted online via REDCap.

Follow-up questionnaires will involve initial contact via email with a link to an online survey. Embedded links will provide the option of responding to the outcome measure assessed in that survey (at 2-month follow-up, medication use; at 7-month follow-up, 6-month continuous abstinence) in a single click. Three attempts will be made one day apart for each follow-up. Follow-up will be attempted at all follow-up points regardless of success at a previous point. A mailing system will be used for the e-mails to enable assessment of whether the e-mail will be (a) delivered versus hard bounce (i.e. permanent delivery problem) versus soft bounce (i.e., temporary delivery problem) and (b) opened.

Invitations and contacts will be structured according to evidence-based methods for maximisation of response rate (26, 27). All invitations will mention incentives for responding.

In order to boost the response rate for the 2-month and 7-month follow-ups, participants who provide their phone number in the baseline questionnaire and consent to receiving text messages and phone calls, will receive first a text message and then a phone call asking them to reply yes or no in order to record their response to the outcomes; medication use at 2-month follow-up and 6-month continuous abstinence at 7-month follow-up.

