Participants who report 6-month continuous abstinence at the 7-month follow-up will be asked to measure their CO levels to verify their abstinence. This will be conducted via a video call with a researcher, using a CO monitor provided by the study team.

Debriefing will involve an e-mail sent after immediate completion of the final follow-up. It will thank participants for their help with the study and provide them with a contact e-mail for further information.

Withdrawal of participants

Participants will be informed that they may withdraw from the study at any time without giving a reason. Unless they withdraw consent, they will be followed up irrespective of smoking outcome or protocol violation. On the basis of the intention-to-treat principle, those who do not respond to endpoint follow-up attempts will be retained in the analyses. Their outcomes will be imputed using multiple imputation (and classified as non-medication users and continuing smokers in a sensitivity analysis). Participants who indicate that they no longer wish to take part in the study will be excluded from the analyses.

Analyses

Primary analyses: Medication use

The primary two comparisons will be as follows:

- Any versus no specific medication recommendation: The first primary analysis will compare the combined medication recommendation arms (varenicline and cytisine) to the control arm (no specific medication recommendation). This analysis will assess whether recommending any medication (varenicline or cytisine) increases medication use.
- Cytisine versus Varenicline recommendation: The second primary analysis
 will compare the cytisine recommendation arm to the varenicline
 recommendation arm among participants randomised to receive a
 medication recommendation. This analysis will determine if there is a
 difference in medication use between the two recommended
 medications.

Logistic regression will be used to model the binary outcome of medication use (yes/no), adjusting for covariates (sociodemographic and smoking-related characteristics at baseline). P-values will be calculated using Wald's test.

The models will include the treatment arms as predictors. To obtain marginal risk ratios (RR) and risk differences (RD) alongside 95% confidence intervals, we will use the *marginaleffects* package in R.

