To account for missing outcome and covariate data, we will use multiple imputation with chained equations (in *mice* package). Imputation models will include experimental group, covariates, self-reported abstinence, and biochemically-validated abstinence. We will assume data are missing at random (MAR), meaning that having missing data on a variable does not depend on the true value of the variable, after accounting for predictor variables included in the imputation model. If less than 10% of data are missing, we will create 5 sets of imputations; otherwise, we will create 20 sets of imputations. Each set will be analysed separately and estimates combined using Rubin's rule.

Secondary analysis: Smoking abstinence outcomes

Above analyses will be repeated for smoking cessation outcomes, defined above in the measures section. As with the primary outcome, multiple imputation using chained equations (the *mice* package in R) will be used to account for missing outcome and covariate data.

Smoking cessation data are often missing not at random, as people who relapse to smoking are generally less likely to complete follow-up. However, the usual way to account for missing not at random, assuming "missing=smoking" (where all individuals with missing follow-up data are assumed to have relapsed to smoking), has been shown to be too extreme in internet-based smoking cessation trials (28). Instead, sensitivity analyses will examine the degree to which violations in the MAR assumption affect results. Multiple imputation with delta-adjustment will be used, with the degree of adjustment ranging from none (delta=0; MAR analysis) to very large (delta=100, approximating the missing=smoking assumption).

	Simple unadjusted complete case and "missing=smoking" analyses will be included in supplementary files as these are often used in meta-analysis.					
	Cost effectiveness					
	First, we will use the smoking cessation outcome directly observed in this trial—comparing the proportion of participants who report having quit smoking across trial arms at follow-up. This will provide a trial-based estimate of the intervention's impact on quitting, which can be used to estimate the potential health benefits (e.g., quality-adjusted life years [QALYs] gained) associated with the intervention.					

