Past year/2 months/6 months quit attempts		Х	х	х

Past/ current use of smoking cessation		x	x	х
medication				
Sustained abstinence			Х	х
Medication use			Х	
Medication uptake			Х	
Breath sample				х
Smoke Free app use			х	х

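### The imputation model for missing 2-month medication use leaves out the medication report scheduled at 7 months

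*Protocol*

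**What the plan says.** - **Outcome** (Protocol, Measures, Outcomes): "The primary outcome will be percentage of participants reporting medication use (varenicline or cytisine use) at the 2-month follow-up".
- **Imputation predictors** (Analyses, Primary analyses: Medication use): "Imputation models will include experimental group, covariates, self-reported abstinence, and biochemically-validated abstinence". The same section describes the outcome model as "adjusting for covariates (sociodemographic and smoking-related characteristics at baseline", so the word covariates does not reach a follow-up item. It also defines missing at random as conditional on the predictors in the imputation model.
- **Non-responders** (Withdrawal of participants): "Their outcomes will be imputed using multiple imputation (and classified as non-medication users and continuing smokers in a sensitivity analysis". Coding as non-use is therefore a sensitivity analysis; the main analysis imputes.
- **Later contact** (Procedure): "Follow-up will be attempted at all follow-up points regardless of success at a previous point".
- **Schedule** (Table 1): the row beginning "Past/ current use of smoking cessation" is marked at allocation, 2 months and 7 months. The separate rows for medication use and medication uptake are marked at 2 months only.

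Nothing says what role a 7-month medication report plays when the 2-month answer is absent.

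**The concern.** A participant can miss the 2-month survey, complete the full 7-month questionnaire, and there report whether they have used a cessation medication. The listed model would still draw that person's 2-month use from arm, baseline characteristics and abstinence alone, as if nothing had been reported.

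This bears on both primary comparisons. Non-response may well be related to use: someone who ignored the recommendation may be less inclined to answer a survey about it. If so, a model that knows little about use beyond arm mostly reproduces the responders' rates. The 7-month item is the one scheduled later measurement of the same behaviour, so it can do most to make missing at random credible. For medication use, the only stated departure from that assumption is the extreme one in which every missing answer is non-use. Graded delta-adjustment is described under the smoking outcomes only.

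**Working it through.** **1. The plan's own figure.** Sample size section: 10% v 16.8%, 2:1, 80% power, two-sided 0.05. With the arcsine effect size, h = 2·asin(√0.168) − 2·asin(√0.10) = 0.2011. Control n = 1.5 × (1.960 + 0.842)² / h² = 291.01, rounded up to 292, so 876 in all (power 80.1%). The figure reproduces. It counts 2-month completers, so the present point does not change it.

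**2. Inputs.** From the Protocol: 10% and 16.8%. Assumed, because the Protocol gives none of these:
- 40% missing at month 2;
- a share s of non-responders giving a 7-month medication report, from 5% to 40%;
- a 7-month report that picks up 85% of true 2-month users and is positive in 3% of non-users (false or late use);
- non-responders in the intervention arms using at half the responders' rate (8.4%), and control non-responders at 10%.

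**3. People affected.** 876 / 0.6 = 1,460 randomised, 584 of them missing. Then 584 × s gives 29, 88, 175 and 234 people at s = 5%, 15%, 30% and 40%.

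**4. What one report tells.** Without it, intervention-arm use is drawn at about 16.8%. With it:
- after a yes: 0.168 × 0.85 / (0.168 × 0.85 + 0.832 × 0.03) = 85%;
- after a no: 0.168 × 0.15 / (0.168 × 0.15 + 0.832 × 0.97) = 3%.

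**5. Bias under the assumed mechanism.** Full-data risk ratio: (0.6 × 16.8 + 0.4 × 8.4) / 10 = 1.344. As listed, non-responders receive the responders' rates, giving 16.8 / 10 = 1.68 (1.69–1.71 in simulation). The excess is 0.336.

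With the report added, non-responders who are seen at month 7 say yes with probability 0.084 × 0.85 + 0.916 × 0.03 = 0.0989. Their mean imputed rate is q = 0.0989 × 0.851 + 0.9011 × 0.0303 = 0.1115. Those not seen receive the pooled rate π, so π = (0.6 × 0.168 + 0.4·s·q) / (1 − 0.4(1 − s)). The control rate stays at 10%. This is a large-sample approximation that takes covariates and abstinence as uninformative about use.

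| s | π | Risk ratio | Share of excess removed |
|---|---|---|---|
| 5% | 0.1662 | 1.66 | 5% |
| 15% | 0.1629 | 1.63 | 15% |
| 30% | 0.1586 | 1.59 | 28% |
| 40% | 0.1561 | 1.56 | 35% |

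**6. Simulation on the same assumptions.**
- 200 replicates, 10 imputations, 65% of 2-month responders also answering at month 7. At s = 30%, 1.69 falls to 1.58, removing (1.69 − 1.58) / (1.69 − 1.34) = 31%. At s = 40%, 1.70 falls to 1.57. The full-data ratio in that run came out at 1.38 by chance; against the exact 1.344 the share removed is 0.13 / 0.356 = 37%.
- 150 replicates, no baseline covariates. At s = 40%, 1.70 falls to 1.58, removing 0.12 / 0.36 = 33%. At s = 30%, 1.71 falls to 1.60, removing 0.11 / 0.37 = 30%. At s = 15% about a tenth is removed, and at s = 5% about 5%.

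**7. If data are missing at random.** There is no bias either way. The standard error of the log risk ratio falls from 0.206 to 0.193 (6%, at s = 30%) in the first simulation and from 0.203 to 0.195 (4%) in the second.

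**The case against.** The case against has real substance.

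- **The content of the 7-month item is not shown.** That it names varenicline and cytisine is inferred from the baseline version. No recall window is given. The neighbouring quit-attempt row in Table 1 mentions six months; a six-month window at month 7 would miss use confined to the first month and include use begun after month 2. Open-ended past use could even reach back beyond the 12 months covered by the exclusion criterion. This stands. It is why the report can only be a predictor and why its window needs to be set.
- **Few reports may exist.** At 7 months the single-click, text and phone routes capture abstinence only, and the people concerned have already missed a survey that carried a larger voucher. This stands, and it makes the lower rows of the table quite possible.
- **The bias mechanism is assumed.** Under the Protocol's own missing-at-random assumption the gain is precision only. This stands.
- **The list need not be closed, and an analysis plan could extend it.** The text does not say that only these variables are used. But the Protocol chose to name the follow-up variables it would use, and named abstinence while omitting the later measure of the outcome behaviour. That is a choice already stated and open to improvement, not detail left for later.

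Three stronger readings are not supported. A reader might infer that the primary analysis counts non-responders as non-users; the Protocol confines that to a sensitivity analysis. A reader might infer that primary-outcome data are being discarded; the outcome is use reported at 2 months, and what goes unused is an auxiliary variable. A reader might want the missing = non-user analysis to score people by their 7-month report; that would mix a 2-month with a 7-month window and blunt a deliberately extreme scenario, when later-starting use is the very reason not to substitute the report.

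**Conclusion.** The point holds as an improvement to the main analysis. The stated imputation model omits a scheduled later report of the same behaviour, for people the trial will still try to reach, while relying on an assumption conditional on that model's predictors. The Protocol does not contradict itself here, and the target of 876 stands.

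The benefit depends chiefly on how many 2-month non-responders complete the 7-month medication item. With 40% missing and intervention-arm non-responders using at half the responders' rate, about a third of the excess over 1.34 is removed if 30–40% do so. At 15% recapture the share is about a tenth by simulation and 15% by the large-sample formula; at 5% it is about 5%. Most of the bias would remain in every case, so this is a partial remedy. If data are missing at random, the gain is about 4–6% in standard error. All of these figures rest on the assumed attrition, recapture and report accuracy.

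**What to change.** Add 7-month reported use of varenicline or cytisine to the imputation model for 2-month medication use, as an auxiliary predictor and never as a substituted outcome value. Set the item's recall window to cover use since enrolment, and have it identify the two drugs. Make the change before anyone is unblinded. Leave the missing = non-user sensitivity analysis unchanged.

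The cost is one more variable in the chained equations and a check of the 7-month question's wording; no new contact is needed. The drawback is that recall at 7 months is imperfect and may include use begun after month 2. As a predictor, the item is calibrated against participants who answered at both times, so such error mainly weakens its contribution and does not put wrong outcome values into the data.

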Power calculations were conducted using the *pwr* package in R. Assuming that 10% of participants in the control arm will report using a prescription smoking cessation medication (based on Smoking Toolkit Study data)(19) at 2-month follow-up, and that a digital recommendation will increase this to 16.8% (relative risk = 1.68), we estimate that at least 876 participants providing data on the primary outcome (i.e., reporting medication use or non-use at 2-month follow-up) would be required to detect this difference with 80% power, using a two-sided alpha of 0.05. This corresponds to 292 participants per arm in the 1:1:1 randomised trial, which is equivalent to a 2:1 ratio of participants receiving any medication recommendation (cytisine or varenicline) versus no recommendation (control).

Using these same sample sizes of primary outcome completers, we also estimated the minimum detectable effect size for the secondary comparison of medication use between the cytisine and varenicline recommendation arms. Assuming a 16.8% average medication use rate across the two groups and setting alpha to 0.05, the smallest detectable relative risk with 80% power is approximately 1.69 with 292 participants per group. These correspond to medication use rates of approximately 21.1% in the cytisine

	arm and 12.5% in the varenicline arm, an absolute difference of 8.6 percentage points.
	Recruitment will continue until at least this number of participants have
	provided data on the primary outcome (medication use at 2-month follow-
	up), in order to ensure adequate power for the primary analysis.
	Power to detect analogous effects on secondary smoking cessation outcomes
	will be lower due to loss to follow-up and expected low rates of quitting.
Recruitment	Participants will be recruited through the Smoke Free app.
	Participants will self-enrol into the study using a link that they will receive
	when they sign up to Smoke Free app (both to the free and premium version
	of the app) and will complete a web-based screening questionnaire, which
	assesses the inclusion and exclusion criteria.
	Participants will be informed that the study involves completing an initial
	online questionnaire (baseline questionnaire) and further online
	questionnaires two and seven months later (follow-up questionnaires).
Compensation	Participants will be informed at baseline that they will receive a £10 gift
Compensation	voucher upon completion of the 2-month follow-up, with an additional £5 if

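### The 5-or-20 imputation rule takes no account of missingness above 10%, so a moderately borderline primary p-value could depend on the random seed (minor; validity is unaffected).

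*Protocol*

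**What the plan says.** Under Analyses (Primary analyses: Medication use), missing outcome and covariate data are handled by chained-equations imputation, and the number of imputations is fixed by a two-step rule: "If less than 10% of data are missing, we will create 5 sets of imputations; otherwise, we will create 20 sets of imputations". Then: "Each set will be analysed separately and estimates combined using Rubin's rule". For the test: "P-values will be calculated using Wald's test". The Measures section makes this the main analysis: "Multiple imputation will be used to account for missing outcome data". Counting non-responders as non-users is a sensitivity analysis only.

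Under Sample size, the target is "at least 876 participants providing data on the primary outcome", and recruitment continues until at least that many have answered. The protocol gives no expected attrition rate and no ceiling on the number randomised. Under Withdrawal of participants, non-responders stay in the analysis and are imputed; only those who no longer wish to take part are removed.

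**The concern.** The rule has one step, at 10%, and none above it. Because recruitment is driven by completers, the missing share is whatever is left over, and it has no upper limit. Imputation noise in the pooled estimate grows with the fraction of missing information and shrinks with the number of imputations. If the first is open-ended and the second is fixed at 20, the noise may not be small beside the standard error.

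In that case two analysts could run the same pre-specified analysis on the same data and fall on opposite sides of 0.05 for a primary comparison. This applies to both primary comparisons, since both use the same imputation and test.

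The threshold is also loosely worded, because the rule does not say whether data means the primary outcome or all cells. Baseline is completed before randomisation, so baseline cells should be nearly full and could dilute a large outcome loss to below 10%.

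**Working it through.** **Inputs from the protocol.** 10% use in control, 16.8% with a recommendation, 292 against 584 completers, 80% power, two-sided alpha 0.05, m = 5 or 20, Rubin's rules, Wald test.

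**Assumed.** Missing share of the primary outcome: 8% or 9% for m = 5, and 20 to 50% for m = 20. With 876 completers, 20% missing means 876/0.8 = 1,095 randomised, and 50% means 876/0.5 = 1,752.

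**The plan's own figure.** With the arcsine effect size used by the R pwr package, h = 2·asin(√0.168) − 2·asin(√0.10) = 0.2011. This requires 291.0 controls, or 873 in total. At 876 the power is 80.1%, so the stated sample size reproduces and is not in question.

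**Size of the noise.** Monte Carlo error of the pooled estimate, as a share of its standard error, is about √(FMI/m), where FMI is the fraction of missing information.
- m = 5, FMI 10%: √(0.10/5) = 14%
- m = 20, FMI 20%: √(0.20/20) = 10%
- m = 20, FMI 50%: √(0.50/20) = 16%
- m = 100, FMI 50%: √(0.50/100) = 7%

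**Set against the distance from the threshold.** Fix 29/292 users in control.
- With 88/584 in the recommendation arms, log OR = ln(88/496) − ln(29/263) = 0.476 and SE = √(1/88 + 1/496 + 1/29 + 1/263) = 0.227. So z = 2.09 and p = 0.036. The distance to 1.96 is 0.13, about the same size as the noise at m = 20.
- With 98/584 (the design effect), log OR = 0.604 and SE = 0.225. So z = 2.69 and p = 0.007. The distance is 0.73, more than four times the noise even at FMI 50%.

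**Simulation over seeds.** Observed data were held fixed, missing outcomes imputed within arm, log odds ratios pooled by Rubin's rules, with 4,000 seeds per setting. If a share s of seeds gives p < 0.05, two seeds disagree with probability 2s(1 − s). For example, m = 20 with 50% missing gives s = 0.64, and 2 × 0.64 × 0.36 = 46%.

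Share of seed pairs that disagree, complete-case p = 0.036:

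| Missing | Plan's m | Plan | m = 100 |
|---|---|---|---|
| 8% | 5 | about 32% | 0% |
| 20% | 20 | about 26–28% | about 2% |
| 50% | 20 | about 46% | about 19% |

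With m = 20, 30% missing gives 36% and 40% missing gives about 42%.

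Other starting points:
- Complete-case p = 0.027 (90/584), m = 20: 5% of pairs disagree at 20% missing and 30% at 50% missing. With m = 100 at 50% missing it is 2%.
- Complete-case p = 0.007 (design effect): 0% for m = 5 at 9% missing and for m = 20 up to 40% missing, and about 1% for m = 20 at 50%.
- Complete-case p = 0.049 (86/584): the middle 95% of pooled p-values is 0.027–0.095 (m = 5, 8% missing) and about 0.018–0.126 (m = 20, 50%). About half of pairs disagree whatever m is, including m = 200.
- Second primary comparison, 58/292 against 40/292 (p = 0.047), m = 20, 40% missing: range 0.019–0.109.

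**The undefined threshold.** The protocol lists about 12 baseline items. Add three outcomes, each assumed 50% missing, and take baseline as complete: (3 × 0.5)/15 = 10% of cells. Outcome loss just under 50% could therefore still select m = 5. At 40% outcome loss and m = 5, the noise is √(0.40/5) = 28% of the standard error.

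**The case against.** The case for leaving the rule alone is substantial, and most of it stands.

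- **Validity.** A reader might infer that 5 or 20 imputations make the primary test wrong. They do not. Rubin's rules charge the finite-m noise to the variance through the (1 + 1/m) term. Simulated type I error with 10% in both groups was 4.9% (m = 5, 8% missing), 4.8% (m = 20, 20%) and 4.9% (m = 20, 50%). Power at the design effect was 77.4%, 77.9% and 76.4%, against 79.1% with m = 200 at 50% missing, so the largest loss shown is about 3 points.
- **Missingness is not known to be high.** A reader might infer that the trial expects 40 or 50% loss. The protocol gives no figure, and it plans against loss with vouchers, single-click replies, repeated emails, texts and calls. The higher scenarios are assumptions.
- **Common rules of thumb are partly satisfied.** Setting m to at least 100 × FMI makes 20 enough up to about 20% missing. A rule holding the variability of the standard error to 5% makes 5 enough below 10% and 20 enough up to about 30%.
- **The simulation uses arm only.** Baseline covariates and abstinence are in the planned imputation model and could lower the FMI, so the figures lean high.
- **No m rescues p = 0.049.** This is correct. The benefit lies a little further from the threshold.
- **No seed or Monte Carlo error report is named.** A reader might count these as defects. They are ordinary details for the analysis plan or code, and that plan is not at hand, so they are not findings.

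What remains is that the protocol does state the 5/20 rule, that it does not respond to the missing share above 10%, and that for a moderately borderline result a larger m visibly improves stability.

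**Conclusion.** The point holds as a minor one about reproducibility, with a small gain in power. It does not show bias, an inflated error rate or an invalid analysis. At the planned effect the conclusion is essentially the same under any seed. For a complete-case p near 0.036, and if 20 to 50% of outcomes are missing, the plan's 20 imputations leave roughly a one-in-four to nearly one-in-two chance that two seeds disagree. Below 10% missing, 5 imputations leave about one in three. These sizes rest on the assumed missing shares, on 876 completers split 292 to 584, and on imputation from arm alone.

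**What to change.** Replace the two-step rule with either of these:
- a single larger number of imputations for all cases, for example at least 100; or
- a number tied to the primary outcome, at least equal to the percentage of missing information, with a floor well above 5.

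If any threshold is kept, state that the percentage refers to the 2-month medication-use outcome and not to all cells.

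In the p = 0.036 case, 100 imputations cut seed disagreement to about 2 to 19% at 20 to 50% missing, and to 0% at 8%. Tying m to the percentage of missing information gives fewer imputations (about 50 at 50%), so it stabilises less than a flat 100. Neither option removes the dependence when p is almost exactly 0.05. The cost is one sentence in the protocol and computing time.
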